### 8.3.13. Interaction between Demographic Variables and SER

Tertiary analyses will be performed on differences between select demographic variables (age 6 – 8 years versus 9 – 10 years; baseline SER -0.50 to -3.00 D versus -3.01 to 6.00 D SER; Asian versus non-Asian; dark irides versus light irides, region (U.S. versus E.U.); female versus male) and change from baseline in SER at Month 12, Month 24, and Month 36. The analysis method will be the same as the primary or secondary efficacy analysis as described in 8.1.1 and 8.2.1 respectively above, except for the addition of the particular demographic variable being analyzed and an associated treatment interaction term. Testing of the difference in demographic variable and the demographic variable by treatment interaction term will be provided. The tertiary analysis will be performed using the mITT set only.

For the purpose of analysis of irides, light irides will consist of Grade 1 – Grade 3 iris colors while dark irides consist of Grade 4 and Grade 5 iris colors. Similarly, for the analysis of race, Asian will be defined as Japanese, East Asian, and South Asian. Non-Asian races will consist of all other non-missing races.

Summary statistics will be presented along with a full data listing by treatment group.

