#### **6.6. Subgroups**

Subjects are randomized based on two stratifications. The first stratification is by age (subjects < 9 years; subjects ≥ 9 years); the second is by refractive error (less myopic: SER -0.50 to -3.00 D; more myopic: one or more eyes with SER -3.01 to -6.00 D). The primary and secondary analyses will be repeated for each stratification.

Additional subgroup exploratory analyses will be performed differences between select demographic variables (Asian versus non-Asian; dark irides versus light irides; female versus male) and change from baseline in SER at Month 12, Month 24, and Month 36.

This document is confidential.

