## 8.1. Primary Efficacy Endpoint and Analysis

### 8.1.1. Primary Efficacy Endpoint

The primary efficacy endpoint is the between-treatment group (Atropine Sulfate Ophthalmic Solution, 0.02% versus Vehicle) difference in the proportion of subjects' eyes who show less than 0.5 D myopia progression (SER) from baseline at the Month 36 visit.

Spherical equivalent refraction will be measured using cycloplegic autorefractometry at Months 6, 12, 18, 24, 30, and 36. Subjects' eyes will be determined at each visit if they have a less than 0.5 D myopia progression (SER). All data collected through Month 36 will be used, regardless of when treatment is stopped. There will be no imputation for missing data; analysis will be conducted as observed.

The primary analysis will be performed using a Mixed Model based on the binomial distribution using a logit link function. Progression as the dependent variable, subject, treatment, visit, eye (left or right) and baseline age group (as randomized) and SER (as randomized) as independent variables and treatment by visit interaction term included. Random intercepts for subject and eye within subject will be included using variance components and compound symmetry covariance structures, respectively. The primary analysis will be performed using the mITT analysis set assuming data is missing at random.

```
proc glimmix data=master empirical method=quad;  
  class subjid trtpn(ref='0') avisitn eye agegr1 sergr1;  
  model eff(event='1') = trtpn avsitn eye agegr1 sergr1 trtpn*avisitn / dist=bin link=logit solution or;  
  nloptions tech=nrridg maxiter=25;  
  random intercept / subject=subjid type=vc;  
  random intercept / subject=eye(subjid) type=cs;  
  estimate '0.02% vs. Pbo Month 36' trtpn 0 1 -1 trtpn*avisitn 0 0 0 0 0 0 0 0 0 0 1 0 0 0 0 0 -1;
```

The absolute risk difference and associated Wald 95% CI will also be presented at Month 36 using the following frequency procedure.

```
proc freq data=dat order=data;  
  tables trtpn*eff / riskdiff(equal cl=wald);
```

Counts and percentage of subject' eyes progressing at each visit for each stage will be summarized. For the primary endpoint and associated secondary endpoints, Odds Ratios, 95% confidence interval (CI), and p-value will be provided along with an accompanying figure.

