8.3.12. Between-treatment Group (Atropine Sulfate Ophthalmic Solution, 0.01% versus Vehicle) Difference in the Proportion of Subjects who Progressed to High Myopia (SER -6.00 D or more myopic) at the Month 36 Visit

A tertiary analysis will be performed on the between-treatment group (Atropine Sulfate Ophthalmic Solution, 0.1% versus vehicle) difference in the proportion of subjects who progressed to high myopia (SER -6.00 D or more myopic) at the Month 36 visit. Progression to high myopia is defined as either of a subject's eyes progressed to high myopia at any time during a visit window.

Results will be presented as results and by baseline myopia stratification. The overall analysis will be performed using a Mixed Model based on the binomial distribution using a logit link function. Progression as the dependent variable, subject, treatment, visit, and baseline age group (as randomized) and SER (as randomized) as independent variables, treatment by visit, treatment by SER (as randomized) and treatment by visit by SER (as randomized) interaction terms included. Random intercepts for subject will be included using variance components. The analysis will be performed using the mITT analysis set assuming data is missing at random.

```
proc glimmix data=master empirical method=quad;  
  class subjid trtpn(ref='0') avisitn agegrp1 sergrp1;  
  model eff(event='1') = trtpn avsitn agegrp1 sergrp1 trtpn*avisitn trtpn*sergrp1 trtpn*avisitn*sergrp1 /  
  dist=bin link=logit solution or;  
  random intercept / subject=subjid type=vc;  
  estimate '0.02% vs. Pbo Month 36' trtpn 0 1 -1 trtpn*avisitn 0 0 0 0 0 0 0 0 0 0 0 0 1 0 0 0 0 0 -1;
```

This document is confidential.

*estimate '0.02% vs. Pbo Month 36 Low ' trtpn 0 1 -1 trtpn\*avisitn 0 0 0 0 0 0 0 0 0 0 0 0 1 0 0 0 0 0 -1  
trtpn\*avisitn\*blmymop 0 1 0 0 0 0 0 -1 0;*

*estimate '0.02% vs. Pbo Month 36 High ' trtpn 0 1 -1 trtpn\*avisitn 0 0 0 0 0 0 0 0 0 0 0 0 1 0 0 0 0 0 -1  
trtpn\*avisitn\*blmymop 0 1 0 0 0 0 0 -1;*

Summary statistics will be presented along with a full data listing by treatment group.

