This document is confidential.

Header	Table Number	Name	Analysis Set
	14.2.3.3.2	Analysis of the New Prescriptions Given After the Start of Treatment due to Progression, at Month 36 Cochran-Mantel-Haenszel Test	Stage 1 Intent-to-Treat Set
14.2.3.4		Subjects who Progressed to High Myopia (Normalized SER -6.00 D or more myopic) at Month 36	
	14.2.3.4.1	Analysis of the Proportion of Subjects who Progressed to High Myopia (Normalized SER -6.00 D or more myopic) at Month 36 by Baseline Myopia Mixed Effects Model	Stage 1 Modified Intent-to-Treat Set
	14.2.3.4.2	Analysis of the Proportion of Subjects who Progressed to High Myopia (Normalized SER -6.00 D or more myopic) at Month 36 by Baseline Myopia Mixed Effects Model	Stage 1 Intent-to-Treat Set
14.2.3.5		Interaction between Demographic Variables and Normalized SER	
	14.2.3.5.1.1	Analysis of the Change from Baseline in Normalized SER (D) in Stage 1 by Treatment Group and Visit (6-8 years old vs. 9-10 years old) Mixed Effect Model	Stage 1 Modified Intent-to-Treat Set
	14.2.3.5.1.2	Summary of the Change from Baseline in Normalized SER (D) in Stage 1 by Treatment Group and Visit (6-8 years old vs. 9-10 years old)	Stage 1 Intent-to-Treat Set
	14.2.3.5.2.1	Analysis of the Change from Baseline in Normalized SER (D) in Stage 1 by Treatment Group and Visit (Baseline SER -0.50 to -3.00 D versus -3.01 to -6.00 D D) Mixed Effect Model	Stage 1 Modified Intent-to-Treat Set
	14.2.3.5.2.2	Summary of the Change from Baseline in Normalized SER (D) in Stage 1 by Treatment Group and Visit (Baseline SER -0.50 to -3.00 D versus -3.01 to -6.00 D D)	Stage 1 Intent-to-Treat Set

This document is confidential.

Header	Table Number	Name	Analysis Set
	14.2.3.5.3.1	Analysis of the Change from Baseline in Normalized SER (D) in Stage 1 by Treatment Group and Visit (Asian vs. Non-Asian) Mixed Effect Model	Stage 1 Modified Intent-to-Treat Set
	14.2.3.5.3.2	Summary of the Change from Baseline in Normalized SER (D) in Stage 1 by Treatment Group and Visit (Asian vs. Non-Asian)	Stage 1 Intent-to-Treat Set
	14.2.3.5.4.1	Analysis of the Change from Baseline in Normalized SER (D) in Stage 1 by Treatment Group and Visit (Dark Irides vs. Light Irides) Mixed Effect Model	Stage 1 Modified Intent-to-Treat Set
	14.2.3.5.4.2	Summary of the Change from Baseline in Normalized SER (D) in Stage 1 by Treatment Group and Visit (Dark Irides vs. Light Irides)	Stage 1 Intent-to-Treat Set

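### The SAP 8.3.13 subgroup model cannot give the Month 12, 24 and 36 interactions: its one treatment-by-subgroup term holds the between-subgroup difference constant over visits

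*SAP*

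**What the plan says.** SAP 8.3.13 lists six factors (age, baseline SER, race, iris colour, region, sex) and ties them to "change from baseline in SER at Month 12, Month 24, and Month 36". The model is that of 8.1.1 or 8.2.1, "except for the addition of the particular demographic variable being analyzed and an associated treatment interaction term". On testing it says: "Testing of the difference in demographic variable and the demographic variable by treatment interaction term will be provided".

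The base model in 8.1.1 has treatment, visit, eye, age stratum and SER stratum, "as independent variables and treatment by visit interaction term included". Its visits are fixed by this sentence: "Spherical equivalent refraction will be measured using cycloplegic autorefractometry at Months 6, 12, 18, 24, 30, and 36".

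The Index of Tables (section 16) plans mixed-model outputs for each factor on change in SER and on the responder endpoint, titled for example "by Treatment Group and Visit (6-8 years old vs. 9-10 years old").

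SAP 8.3.12, the section immediately before, deals with progression to high myopia by baseline myopia. There the model is written with "treatment by visit, treatment by SER (as randomized) and treatment by visit by SER (as randomized) interaction terms included".

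SAP 6.6 says of the randomisation strata: "The first stratification is by age", split at 9 years. The second is by refractive error. The main analyses are repeated within each stratum.

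**The concern.** Three visit-specific interactions are in view, but the model has one interaction coefficient per active arm. With no subgroup-by-visit and no treatment-by-subgroup-by-visit term, the model assumes that whatever separates, say, Asian from non-Asian children in their response to atropine is fully present at Month 6 and does not change afterwards. Any difference between subgroups in the vehicle arm is held constant over visits in the same way.

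Change from baseline starts at zero by construction, so a constant between-subgroup difference is a strong assumption over three years. If it fails, the reported interaction describes no particular visit. A reader who takes it as the Month 36 interaction may be misled about whether the treatment works differently in some children.

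A second, smaller problem is that the age factor enters the model twice.

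**Working it through.** **1. Figures in the plan.** The documents give no size or time course for any subgroup interaction, so there is no stated figure to reproduce. What follows rests on the model structure and on assumed time courses.

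**2. What the single term estimates.** Let d(t) be the true between-subgroup difference in treatment effect at visit t. The protocol synopsis (Statistical Analyses) gives the continuous model random intercepts for subject and eye. With that structure and complete data, the generalised least squares coefficient of a constant treatment-by-subgroup term is the plain mean of d(t) over the visits in the model. Here these are Months 6, 12, 18, 24, 30 and 36.

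**3. Linear growth from zero, d(t) = d·t/36.**
- Mean month = (6+12+18+24+30+36)/6 = 126/6 = 21, so the term estimates 21/36 = 0.583 of d.
- Month 36 (true value d): 1 − 0.583 = 0.417, so 42% too small.
- Month 24 (true value 0.667d): 0.583/0.667 = 0.875, so 12.5% too small.
- Month 12 (true value 0.333d): 0.583/0.333 = 1.75, so 75% too large.

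**4. Other assumed time courses, complete data, six visits.**

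| Assumed course of the interaction | Term ÷ Month 36 value | Error at Month 36 |
|---|---|---|
| Quadratic (late) growth | 91/216 = 0.421 | 58% too small |
| Linear growth | 0.583 | 42% too small |
| Square-root growth | 0.737 | 26% too small |
| Complete by Month 24 | 4.5/6 = 0.750 | 25% too small |
| Complete by Month 12 | 5.5/6 = 0.917 | 8% too small |
| Constant | 1.00 | none |
| Peak at Month 12, half of it left at Month 36 | 8.5/6 = 1.417 | 42% too large |

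**5. Dropout.** The protocol expects 27% dropout over Stage 1. Losing 27% evenly by Month 36 shifts weight to the early visits. With linear growth the ratio falls to 0.53–0.54, so the term is 46–47% too small. This was computed with assumed (subject, eye) intra-class correlations of (0.3, 0.1) and (0.6, 0.2).

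**6. Scale.** All these ratios are for continuous SER. In the logit model of 8.1.1 the interaction is on the log-odds scale, and the percentages do not carry over. The constraint itself does.

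**7. Age entered twice.** The mITT set is children aged 6 to 10, and SAP 7.2 truncates age to complete years. In that set, 6–8 against 9–10 years is the same split as under 9 against 9 or over, which is already in the model. Apart from mis-stratified children, the added main effect is aliased and its test has no degrees of freedom. The treatment-by-age interaction remains estimable.

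**8. SER entered twice, conditionally.** The SER stratum is defined per subject (one or more eyes beyond the cut) on un-normalised values. SAP section 8 normalises baseline SER for analysis but not for stratification. By the section 8 formula, at an assumed vertex distance of 12 mm, −3.10 D becomes 100/(100/(−3.10) − 12/10) = 100/(−33.458) = −2.99 D, which crosses the −3.00 D cut. The duplication therefore holds only if the subgroup is the as-randomised stratum.

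**9. Cost of the fuller model.** Subgroup-by-visit: 1 × 5 = 5 parameters. Treatment-by-subgroup-by-visit: 2 × 1 × 5 = 10. Total 15 per two-level factor.

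**The case against.** A reader might infer that the plan understates the Month 36 interaction by about 40%. The documents do not support that as a property of the plan: it requires linear growth from zero, and even the direction reverses if the interaction peaks early and fades. A reader might also infer that subgroup results collapse into one average over time. They do not, because treatment-by-visit stays in the model and only the gap between subgroups is fixed.

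Other analyses fill part of the gap. Repeating the main analyses by stratum (6.6, 8.1.5) gives visit-specific treatment effects for age and SER. The index also plans by-visit summaries for all six factors in the ITT set. But race, iris colour, region and sex have no other visit-specific model, and the SAP describes no interaction test for the summaries.

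A two-way test is a common parsimonious choice, and sparse data are a real difficulty for the responder endpoint. At the planning rate, 7% of 91 vehicle children is about 6 responders before any subgroup split, so three-way logit terms would be fragile. That argues for a simpler Month 36 model there. It does not justify the constraint on continuous SER.

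Finally, the text of 8.2.1 is not in the copy reviewed, so its code could not be checked, and the added term could be read more widely than two-way. The singular wording, the test named in 8.3.13 and the explicit three-way term in 8.3.12 favour the two-way reading.

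**Conclusion.** The point holds as a structural mismatch. As written, 8.3.13 cannot deliver separate Month 12, 24 and 36 interactions for change in SER, and the one it does deliver is a visit-averaged quantity. How far that lies from the Month 36 value is unknown. It is unbiased only if the average happens to equal the Month 36 value, as with a constant interaction, and far too small if the interaction builds up late. Any single percentage must be quoted with its assumed time course.

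The duplication is firm for age and conditional for SER. It affects the main-effect test and leaves the interaction test intact.

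The analyses are tertiary and outside the fixed testing sequence, so no primary or secondary conclusion changes. The correction should be made, because the plan otherwise cannot produce the visit-specific interactions that it sets out to examine.

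**What to change.** In SAP 8.3.13:

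- For change in SER, add subgroup-by-visit and treatment-by-subgroup-by-visit terms, and report interaction contrasts at Months 12, 24 and 36.
- For the responder endpoint, use the same terms where the data allow. Where cells are sparse, fit the subgroup model at Month 36 only, and state the sparseness rule in advance.
- For age, enter the factor once and take the main-effect test from the stratum factor already in the model.
- For SER, state whether the subgroup is the as-randomised, subject-level, un-normalised stratum. If it is, enter it once as for age. If it is normalised or defined per eye, say so and keep it as a separate factor.

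The change needs SAP wording and programming only, with no new data. The price is 15 extra parameters per two-level factor, so the visit-specific interactions will have wider intervals.

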### 8.3.14. Between-treatment Group (Atropine Sulfate Ophthalmic Solution, 0.02% Versus Vehicle) Difference in the Mean Change from Baseline in Crystalline Lens Thickness at the Month 36 visit

A tertiary analysis will be performed on the between-treatment group (Atropine Sulfate Ophthalmic Solution, 0.02% versus vehicle) difference in the mean change from baseline in crystalline lens thickness at the Month 36 visit. The analysis method will be the same as the secondary efficacy analysis as described in 8.2.1 above. The tertiary analysis will be performed using the mITT and ITT sets.

Summary statistics will be presented along with a full data listing by treatment group.

### 8.3.15. Between-treatment Group (Atropine Sulfate Ophthalmic Solution, 0.01% Versus Vehicle) Difference in the Mean Change from Baseline in Crystalline Lens Thickness at the Month 36 visit

A tertiary analysis will be performed on the between-treatment group (Atropine Sulfate Ophthalmic Solution, 0.01% versus vehicle) difference in the mean change from baseline in crystalline lens thickness at the Month 36 visit. The analysis method will be the same as the secondary efficacy analysis as described in 8.2.1 above. The tertiary analysis will be performed using the mITT and ITT sets.

Summary statistics will be presented along with a full data listing by treatment group.

This document is confidential.

8.3.16. Rebound Assessment Based on the Change from Stage 2 Baseline (Month 36) at Months 42 and 48

The change from baseline from Stage 2 baseline (Month 36) to the Month 42 and Month 48 visits will be summarized using descriptive statistics. Summaries will be provided for active treatment Stage 1 subjects who received the same or lower dose, including placebo, Summaries will be provided for Stage 1 and Stage 2 treatment combinations listed:

- Atropine Sulfate Ophthalmic Solution, 0.02% -> Atropine Sulfate Ophthalmic Solution, 0.02%
- Atropine Sulfate Ophthalmic Solution, 0.02% -> Atropine Sulfate Ophthalmic Solution, 0.01%
- Atropine Sulfate Ophthalmic Solution, 0.02% -> Vehicle
- Atropine Sulfate Ophthalmic Solution, 0.01% -> Atropine Sulfate Ophthalmic Solution, 0.01%
- Atropine Sulfate Ophthalmic Solution, 0.01% -> Vehicle

8.3.17. Rebound Assessment Based on the Responders at Months 42 and 48

For subject on active treatment who were responders (subjects' eyes who show less than 0.5 D myopia progression (SER) from baseline at the Month 36 visit) in Stage 1, their progression from Stage 1 baseline at Month 42 and Month 48 will be summarized using count and percentage.

Summaries will be provided for Stage 1 and Stage 2 treatment combinations listed:

- Atropine Sulfate Ophthalmic Solution, 0.02% -> Atropine Sulfate Ophthalmic Solution, 0.02%
- Atropine Sulfate Ophthalmic Solution, 0.02% -> Atropine Sulfate Ophthalmic Solution, 0.01%
- Atropine Sulfate Ophthalmic Solution, 0.02% -> Vehicle
- Atropine Sulfate Ophthalmic Solution, 0.01% -> Atropine Sulfate Ophthalmic Solution, 0.01%
- Atropine Sulfate Ophthalmic Solution, 0.01% -> Vehicle

#### **8.4. Exploratory Efficacy Analyses**

For all Stage 2 exploratory analyses, summary statistics will be provided based on the Stage 1 to Stage 2 treatment description. Analyses table will only include the groups presented in the analyses. The eight treatment groups for these tables will include:

- Atropine Sulfate Ophthalmic Solution, 0.02% -> Atropine Sulfate Ophthalmic Solution, 0.02%
- Atropine Sulfate Ophthalmic Solution, 0.02% -> Atropine Sulfate Ophthalmic Solution, 0.01%
- Atropine Sulfate Ophthalmic Solution, 0.02% -> Vehicle
- Atropine Sulfate Ophthalmic Solution, 0.01% -> Atropine Sulfate Ophthalmic Solution, 0.02%
- Atropine Sulfate Ophthalmic Solution, 0.01% -> Atropine Sulfate Ophthalmic Solution, 0.01%
- Atropine Sulfate Ophthalmic Solution, 0.01% -> Vehicle
- Vehicle -> Atropine Sulfate Ophthalmic Solution, 0.02%
- Vehicle -> Atropine Sulfate Ophthalmic Solution, 0.01%

8.4.1. Between-treatment Group (Atropine Sulfate Ophthalmic Solution, 0.02% versus Vehicle and Atropine Sulfate Ophthalmic Solution, 0.01% versus Vehicle) Difference in the Proportion of

This document is confidential.

Subjects' Eyes with Higher Myopia (SER  $\leq$  -3.00) who Show less than 0.75 D Myopia Progression (SER) From Baseline at the Month 36 Visit

An exploratory analysis will be performed on difference in the proportion of subjects' eyes who show less than 0.75 D myopia progression (SER) from baseline at the Month 36 visit. The analysis method will be the same as the primary efficacy analysis as described in 8.1.1 above.

Summary statistics will be presented by treatment group.

8.4.2. Between-treatment Group Difference in the Mean Change from Study Baseline in SER at the Month 48 Visit.

The analysis will be performed using the same methods as in 8.2.1 above. Only the four indicated arms being test will be included in the analysis model. The analysis will be performed using the mITT analysis set. The following treatment comparisons will be made:

- Atropine Sulfate Ophthalmic Solution, 0.02% -> Atropine Sulfate Ophthalmic Solution, 0.02% vs. Atropine Sulfate Ophthalmic Solution, 0.02% -> Vehicle
- Atropine Sulfate Ophthalmic Solution, 0.01% -> Atropine Sulfate Ophthalmic Solution, 0.01% vs. Atropine Sulfate Ophthalmic Solution, 0.01% -> Vehicle

Summary statistics and figure will be presented along with a full data listing for all treatment groups.

8.4.3. Between-treatment Group Difference in the Mean Change from Stage 2 Baseline (Month 36) in SER at the Month 48 Visit.

The analysis will be performed using the same methods as in 8.2.1 above.

Only the four indicated arms being test will be included in the analysis model. The analysis will be performed using the mITT analysis set. The following treatment comparisons will be made:

- Atropine Sulfate Ophthalmic Solution, 0.02% -> Atropine Sulfate Ophthalmic Solution, 0.02% vs. Atropine Sulfate Ophthalmic Solution, 0.02% -> Vehicle
- Atropine Sulfate Ophthalmic Solution, 0.01% -> Atropine Sulfate Ophthalmic Solution, 0.01% vs. Atropine Sulfate Ophthalmic Solution, 0.01% -> Vehicle

Summary statistics and figure will be presented along with a full data listing for all treatment groups.

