#### **Duration of Treatment:**

The study will be conducted in 2 stages. Stage 1 is the primary safety and efficacy stage of the study and will be 3 years (36 months) in duration. Subjects will be randomized in a 2:2:3 ratio of Vehicle: Atropine Sulfate Ophthalmic Solution, 0.01%: Atropine Sulfate Ophthalmic Solution, 0.02%. On completion of 3 years of treatment, Stage 2, a randomized cross-over stage will commence, and all subjects will be re-randomized to 1 of the 3 study medications and will receive this treatment for 1 year (12 months). Subjects who were randomized to 0.01% or 0.02% Atropine Sulfate Ophthalmic Solution during Stage 1 will be re-randomized in a 1:1:1 ratio to one of the 3 treatment arms (Vehicle: Atropine Sulfate Ophthalmic Solution, 0.01%: Atropine Sulfate Ophthalmic Solution, 0.02%), and subjects who were randomized to Vehicle during Stage 1 will be rerandomized in a 1:1 ratio to active treatment (Atropine Sulfate Ophthalmic Solution, 0.01%: Atropine Sulfate Ophthalmic Solution, 0.01%: Atropine Sulfate Ophthalmic Solution, 0.02%).

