#### **Statistical Analyses:**

The primary and secondary efficacy analyses will be performed using the mITT Set assuming data missing at random.

The primary analysis and any other analysis of binary response measures will be performed using a mixed-effects model based on the binomial distribution using a logit link function. The model will include subject, treatment group, visit, eye (left or right), and baseline age group (as randomized) and SER (as randomized) as independent variables and treatment group-by-visit interaction term included. Random intercepts for subject and eye within subject will be included using variance components and compound symmetry covariance structures, respectively. In addition, sensitivity analyses will be performed for the primary efficacy endpoint to assess the impact of missing data. These sensitivity analyses will be described in the statistical analysis plan.

For comparisons of mean change from baseline for continuous measures, the analysis will be performed using a mixed-effects model with a random intercept. The model will include treatment group, visit, eye (left or right), baseline age group (as randomized), and baseline SER group (as randomized) as independent variables and the treatment group-by-visit interaction. Will be included. The degrees of freedom will be determined using the Kenward-Roger approximation.

Random intercepts for subject and eye within subject will be included using unstructured covariance structures.

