### 6.2. Key Definitions

Treatment-emergent adverse events (TEAEs) of Stage 1 are defined as any new or worsening of existing adverse events that occur or worsen between the first dose date of Stage 1 and the last dose date of Stage 1.

TEAEs of Stage 2 are defined as any AE the occurs or worsens between the first dose date of Stage 2 and the last dose date of Stage 2.

First dose date for Stage 1 is defined as the first dose of study medication received after randomization in Stage 1.

First dose date for Stage 2 is defined as the first dose of study medication received after the Stage 1 last dose date and subject is re-randomized.

For subjects who did not receive study medication in a given stage, leave first dose date for that stage as missing. If the first dose date is missing and if the subject is randomized, impute the missing first dose date using the randomization date in the analysis of Time to Change from Baseline in Myopia Progression of -0.75D (see 8.3.7 and 8.3.8).

Baseline for Stage 1 is defined as the last measurement prior to first dose of study medication in Stage 1, If an adverse event starts or non-study medication taken on the day of first dose it will be treated as occurring after treatment started. All other planned measurements are presumed to occur prior to first dose of study medication.

Baseline for Stage 2 will be defined as latest results prior to start of study medication in Stage 2, which occurs the day after the Month 36 visit. The results of the Month 36 visit will act as the baseline for Stage 2.

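### SAP 8.4.2 tests the Month 36 re-randomisation on four-year SER change with no visible Month 36 covariate: precision is lost (standard error 2.0 times the adjusted one in a simple model, about 1.2 to 4 times in others), without bias

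*SAP*

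**What the plan says.** In SAP 8.4.2, children re-randomised at Month 36 to the same atropine concentration are compared with those switched to Vehicle, separately for each Stage 1 concentration, in the mITT set. The outcome is SER change from study baseline to Month 48. On method: "The analysis will be performed using the same methods as in 8.2.1 above. Only the four indicated arms being test will be included".

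SAP 8.4.3, headed "Difference in the Mean Change from Stage 2 Baseline (Month 36) in SER at the Month 48 Visit", makes the same two comparisons in the same arms and set, with the same instruction: "The analysis will be performed using the same methods as in 8.2.1 above".

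The text of SAP 8.2.1 was not in the copy available for this review. The Protocol Synopsis (Statistical Analyses) describes the model for continuous change as treatment group, visit, eye, "baseline age group (as randomized), and baseline SER group (as randomized) as independent variables", plus treatment by visit. It adds: "Random intercepts for subject and eye within subject will be included using unstructured covariance structures". No Month 36 value is listed. SAP 6.2 nevertheless states: "The results of the Month 36 visit will act as the baseline for Stage 2".

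On timing, the protocol (Duration of Treatment) says: "Stage 1 is the primary safety and efficacy stage of the study and will be 3 years (36 months) in duration". Re-randomisation follows.

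SAP 4.4 lists both endpoints as exploratory and limits them to children on atropine who responded at Month 36. SAP 8.4.2 and 8.4.3 name mITT without that limit.

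**The concern.** The allocation under test is made at Month 36. Three of the four years in the 8.4.2 outcome come before it and cannot be an effect of it. In this contrast they are pure noise, and a chance difference between arms at Month 36 goes into the estimate in full. The value that would remove the noise is already collected, precedes re-randomisation, and is the SAP's own Stage 2 baseline.

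The SAP describes Stage 2 as a way to observe what happens when treatment is changed or stopped (section 3.3). Sections 8.4.2 and 8.4.3 are its only model-based comparisons of stopping; the rebound sections (8.3.16 and 8.3.17) are descriptive. The arms are small. The two sections estimate the same withdrawal effect in expectation, so a disagreement caused only by chance at Month 36 could be read as a finding.

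**Working it through.** **Arm sizes.** The plan states no SD, standard error or power for Month 48. Its Stage 1 figures do reproduce: exact enumeration of Fisher's test for 0.25 versus 0.07 gives 0.956 at 136 and 91 (stated 95%) and 0.901 at 91 and 91 (stated 90%). Drop-out of 27% gives 91/0.73 = 124.7 and 136/0.73 = 186.3 (stated 125 and 186). With 1:1:1 re-randomisation, each Stage 2 sequence in the mITT set has about 186 × 0.73/3 = 45 children (0.02%) or 125 × 0.73/3 = 30 (0.01%).

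**Does the random-intercept model recover the loss?** No. With complete data and a full treatment-by-visit term, a generalised least squares fit with Stage 1 visits included gave a Month 48 contrast of -0.6538 in one simulated data set. The raw difference in Month 48 means was also -0.6538.

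**Variance algebra (assumed model).** Let each yearly true increment have variance 1, let any two increments of a child correlate c, and let each visit carry measurement-error variance r.

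- A = Var(Month 48 change from study baseline) = 4 + 12c + 2r
- B = Var(Month 36 change from study baseline) = 3 + 6c + 2r
- C = Cov(the two changes) = 3 + 9c + r
- Adjusted residual variance = A - C²/B
- Var(Month 48 change from Month 36), the 8.4.3 outcome = 1 + 2r
- Standard-error ratio, 8.4.2 to adjusted = √[A/(A - C²/B)]
- Power of 8.4.2 where the adjusted analysis has 80% = Φ(2.80/ratio - 1.96)

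Example, c = 0 and r = 0: A = 4, B = 3, C = 3, residual 4 - 9/3 = 1, ratio √4 = 2.00. Simulation with 45 per arm and 4,000 runs gave 1.99.

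Example, c = 0 and r = 1: A = 6, B = 5, C = 4, residual 6 - 16/5 = 2.8, ratio √(6/2.8) = 1.46.

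| Assumption | Ratio | Power of 8.4.2 |
|---|---|---|
| c = 0, r = 0 | 2.00 | 29% |
| c = 0.2, r = 0 | 2.65 | 18% |
| c = 0.4, r = 0 | 3.46 | 12% |
| c = 0.5, r = 0 | 4.00 | 10% |
| c = 0, r = 0.25 | 1.74 | 36% |
| c = 0, r = 1 | 1.46 | 48% |
| Month 36 responders only, c = 0, r = 0 | 1.31 | 57% |
| Month 36 and Month 48 changes correlate only 0.5 | 1.155 | 68% |

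The responder row takes the upper 25% of a normal Month 36 change, 25% being the plan's assumed atropine responder proportion. That multiplies the Month 36 variance by 0.2416, and √(3 × 0.2416 + 1) = 1.31. The last row is 1/√(1 - 0.5²). The top of the range depends on stopping at c = 0.5: error-free increments with c = 0.7 would give 5.66.

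In dioptres, with an assumed yearly SD of 0.4 D, c = 0, r = 0 and 45 per arm, the standard error is 2 × 0.4 × √(2/45) = 0.169 D for 8.4.2 and 0.4 × √(2/45) = 0.084 D adjusted.

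**What 8.4.3 already achieves.** Without error, its variance is 1 against an adjusted 1.000, 0.914 and 0.733 at c = 0, 0.2 and 0.4. Its power is then 80.0%, 76.3% and 66.9% against 80%: a loss of none to about 13 points. With c = 0 and r = 0.25 or 1, its standard error is about 1.01 or 1.04 times the adjusted one.

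**Is Month 36 SER alone enough?** Not in 8.4.2, where study-baseline SER enters only as a two-level group. With an assumed within-stratum baseline SD of 0.5 to 1.0 D and yearly SD of 0.3 to 0.5 D (c = 0, r = 0), the standard error falls only by a factor of 1.09 to 1.51.

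**The case against.** The best reply is that 8.4.3 already does the job: same arms, same set, three earlier years subtracted, and no loss if increments are independent. The SAP leans that way elsewhere. Its table index puts the Stage 2-baseline model first, its Stage 2 change figures use that baseline, and so does the rebound summary in 8.3.16. No Stage 2 power is claimed, the objective is only to observe, and both analyses lie outside the fixed sequence in SAP 8. Four-year change is a legitimate quantity to report.

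Most of this stands and keeps the point small. It does not remove it. No section ranks 8.4.3 above 8.4.2, and 8.4.2 remains the model-based analysis of the first-listed exploratory endpoint. 8.4.3 itself gains from adjustment if fast progressors stay fast.

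A reader might infer more than the documents support:

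- That the standard error at least doubles. Two is the exact value for independent, error-free increments, not a floor. Measurement error, restriction to responders or a weaker correlation takes it below two.
- That 8.4.2 is biased. It is not: allocation is randomised at Month 36, and chance imbalance is sampling error that the standard error covers.
- That the plan as a whole would miss an effect of stopping. The low powers in the table belong to 8.4.2 alone.
- That the SAP certainly omits Month 36. With 8.2.1 unseen, the covariate list is inferred from the protocol. SAP 12 lists only vertex-distance normalisation as a change from the protocol, so the inference is reasonable but not certain.

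**Conclusion.** The point holds as a loss of precision in one exploratory analysis. On the visible model, the 8.4.2 standard error is 2.0 times the Month 36-adjusted one under equal, independent, error-free yearly increments, and about 1.2 to 4 times across the other assumptions shown. The variance inputs are all assumed, because the documents supply none. For 8.4.3 the loss is small. The primary and secondary conclusions are untouched.

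The population conflict is a separate defect that bears on the size. If SAP 4.4 governs and 25% respond, the sequences shrink to about 45.3 × 0.25 = 11 and 30.4 × 0.25 = 8 children, and the ratio falls to about 1.3 under independent, error-free increments.

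**What to change.** In SAP 8.4.2 and 8.4.3, add as covariates each eye's normalised Month 36 SER and its change from study baseline to Month 36, with Months 42 and 48 as the outcome visits. Take the Month 36 value as SAP 6.2 defines the Stage 2 baseline, so that it precedes Stage 2 dosing.

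The two outcomes then differ only by a quantity that is itself a covariate, so the treatment contrast is identical. Present it once, as the main Stage 2 comparison, and keep the unadjusted four-year change as a descriptive summary.

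Reconcile the population between SAP 4.4 (Month 36 responders) and 8.4.2 and 8.4.3 (mITT).

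The cost is a short SAP edit and no new data. Children without a Month 36 refraction leave the 8.4.2 model, as they already do in 8.4.3.
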